This study is a preliminary randomized control trial evaluating a 9-week diet and lifestyle intervention on quality of life, patient-reported symptoms, and biomarkers associated with methylation. We will recruit forty-eight participants with 24 randomized to each study group. Refer to Figure 1 for an overview of the study flow.

Figure 1. Study Flow Overview

D.2 Study Intervention

Study participants will be randomized into an intervention or control group. The intervention group will undergo a 3-week washout period following the discontinuation of any non-medically required nutrition or herbal supplements. The intervention group will follow detailed diet and lifestyle recommendations over a 9-week period. Two webinars at the start of the

Protocol

Study Title: Methylation Diet and Lifestyle (MDL) Study

PI: [name], ND, MPH and [name], ND

IRB #: RB100217

Approval Date: 2.9.18

Ver. 1.1

intervention phase will provide information to participants on proper food and exercise choices, as well as how to access and use the required electronic resources (apps).

The control group will undergo the same testing measures as the intervention group, but will not have access to the education information or be instructed to change diet or lifestyle factors. They will have access to the information after the study is complete.

D.2.1 Diet Recommendations

Specific dietary guidelines will be outlined for participants and should include the following:

Per week	Per day

3 servings of liver
 
 • (1 serving = 3 oz) • Choose preferably organic liver 
5-10 eggs
 
 • Ideally free-range, organic, omega-3 enriched 	
2 cups of dark leafy greens
 
 • Measured raw, chopped, and packed • Including kale, Swiss chard, collards, spinach, dandelion, mustard greens • Does not include salad greens such as romaine, iceberg, Spring mix 
2 cups cruciferous vegetables
 
 • Measured raw, chopped, and packed • Including broccoli, cabbage, cauliflower, Brussels sprouts, bok choy, arugula, kale, watercress, rutabaga, kohlrabi, radish, turnip
General	

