
Choose organic at least half of the time.
 
Stay hydrated
 
Don't eat between 7pm and 7am, and at least 2 hours before bed
 
Include healthy oils
 
 • Balance types of fat • E.g. coconut, olive, flaxseed and pumpkin seed oil 
Avoid dairy, grains, legumes/beans
 
Minimize plastic food containers
	
3 cups colorful, low glycemic vegetables of your choosing
 
1-2 medium beet
 
4 tbsp (1/4 cup) pumpkin seeds (or pumpkin seed butter)
 
4 tbsp (1/4 cup) sunflower seeds (or sunflower seed butter)
 
1+ serving methylation adaptogens:
 
 • 1/2 cup berries (wild preferred) • 1/2 tsp rosemary • 1/2 tsp turmeric • 2 medium cloves garlic • 2 cups green tea (brewed 10 minutes) • 3 cups oolong tea (brewed 10 minutes) 
6 oz animal protein
 
 • grass-fed, pastured, organic and hormone/antibiotic-free 
2 servings of low glycemic fruit

These recommendations serve as a guidance, while individual intake may vary based on preference. Throughout the study, participants will be provided 2-week menu plans with recipes for all meals, snacks, smoothies.

Protocol

Study Title: Methylation Diet and Lifestyle (MDL) Study

PI: [name], ND, MPH and [name], ND

IRB #: RB100217

Approval Date: 2.9.18

Ver. 1.1

Refer to Appendix A for detailed nutrition recommendations.

D.2.2 Exercise Recommendations

Participants will be encouraged to exercise a minimum of 30 minutes at least 5 days per week at an intensity of 60-80% of maximum perceived exertion. Possible types of physical activity include, but not limited to, brisk walking, light jogging, hiking, dancing, yardwork, bicycling, and swimming.

D.2.3 Stress Management Recommendations

Participants will utilize the Cleveland Clinic's Stress Free Now application to engage in a variety of guided stress reduction techniques, including meditation and mindful breathing. Recommended frequency is twice daily, preferably morning and evening.

D.2.4. Lifestyle Recommendations

Participants are encouraged to average a minimum of 7 hours of sleep per night.

D.2.5. Study Supplements

Participants will be provided with two supplements. Details on the products are outlined in section D.12 of the protocol. Participants will take 2 servings of PhytoGanix and 2 capsules of UltraFlora Intensive Care probiotic daily, in divided doses.

D.2.6. Control group

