Not all foods recommended and consumed during the study intervention may be captured by VioScreen. An additional food frequency questionnaire (FFQ), with approximately 250 foods and beverages, was created to assess consumption. It has been designed to be consistent with the validated block Brief FFQ by NutritionQuest. This will be administered electronically via RedCap online database to all study participants at Visits 1, 2, and 3.

D.2.7.5. Adherence phone calls

Participants will be contacted via phone once per week during the first 4 weeks of the study and every other week for the remainder of the study. Designated health coaches will assess for adherence to the study intervention including dietary, stress management, and exercise recommendations. Participants will be able to ask questions pertaining to the study intervention.

Refer to Appendix B for detailed script of these phone calls.

Protocol

Study Title: Methylation Diet and Lifestyle (MDL) Study

PI: [name], ND, MPH and [name], ND

IRB #: RB100217

Approval Date: 2.9.18

Ver. 1.1

D.3 Description of Participant Population

D.3.1. Participant Characteristics

Sample size: n=48

We will enroll and randomize up to 48 people which will allow for 20% attrition such that we have an evaluated sample size of 40 to allow for withdraws or dropouts.

Age: 50-72

Gender: Males only

Minorities: all racial and ethnic backgrounds will be recruited from the general population without preference or discrimination.

Vulnerable Populations (e.g. children, pregnant women, cognitively impaired): No vulnerable populations will be enrolled.

D.3.2. Inclusion and Exclusion Criteria

Individuals must meet the following participation criteria:

Inclusion criteria:

- Males, ages 50-72
- Willing to adhere to 9 weeks of a dietary and lifestyle program including specific nutrition and exercise guidelines
- Willing to avoid any over-the-counter medications, supplements or herbal products for the length of the study, except short-term use (<1 week) use at least 1 week before scheduled study visits
- Willing to have blood drawn three times and abstain from food or beverage intake for 10-12 hours before blood draws
- Willing to provide saliva samples
- Willing to track food intake, sleep, stress management techniques, and exercise daily
- Willing to drink a nutrient-enriched beverage and take a encapsulated probiotic daily
- Willing and able to use electronic devices and connect to the internet

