Ver. 1.1

D.4.3. Tertiary Outcome: Changes in methylation at CpG sites of DNA

The tertiary outcome will be the assessment of methylation changes at “CpG” sites on DNA using a commercial available assay kit. CpG sites are sites on DNA in which a cytosine base is separated from a guanine base by only one phosphate; CpG sites are known sites for regulation by methylation. The Infinium MethylationEPIC Kit by Illumina uses the latest technology to assess methylation status of over 850,000 DNA sites across the genome. Using DNA provided from a saliva sample, this assay measured changes in methylation at “CpG” sites of DNA, i.e., whether or not sites for methylation are, or are not, methylated. For a given time point, the degree of methylation at each site (i.e., β) is presented as a color ranging from “green” (i.e., $\beta = 0$, low methylation) to “red” (i.e., $\beta = 1$, high methylation). We will compare the methylation state of participants at baseline to their status at the end of the study. “Differential” methylation is considered a change in CpG site methylation of $\Delta\beta \geq 0.66$. See Figure 2 below for a typical representation of the results of the assay.²⁸

Figure 2: Typical Demonstration of Results Applying the Infinium MethylationEPIC Kit

A saliva sample will collect approximately 2 mL (~1 teaspoon) into a cryovial. Saliva samples will be labeled only with a study ID, date of collection, and visit number and frozen to -70 °C.

At the conclusion of the study, all samples will be batched shipped to: Yale University Center for Genome Analysis Attn: [name], Associate Director of Microarray; [name].

D.4.4. Exploratory Outcomes: Changes in biomarkers associated with methylation

D.4.4.1. Methylation Profile – Doctor’s Data

Protocol

Study Title: Methylation Diet and Lifestyle (MDL) Study

PI: [name], ND, MPH and [name], ND

IRB #: RB100217

Approval Date: 2.9.18

Ver. 1.1

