Participants will be instructed to blend, shake, or briskly stir 1 level scoops of PhytoGanix into 8 ounces of water or juice two times daily. Participants will be instructed to take 2 capsules of UltraFlora intensive Care with 8 ounces of water once a day.

D.7.5. Product Adherence

Participants will be contacted by phone weekly Weeks 1-4 and semi-weekly Weeks 5-8 by the health coach team to check in on their progress. If participants report issues with product adherence product, the health coach team will discuss strategies with the participant to increase adherence. (For example, they may suggest posting note on the refrigerator or keeping the study product jar in a location such as a kitchen counter or dining table in order to incorporate taking the study product into daily routines.)

Adherence will be quantified by the study investigators who will count unused capsules and weigh unused study product after it is returned at the 5 week and 9 week study visits.

D.8. Blood and Saliva Collection and Analysis

Fasting blood samples and saliva samples will be obtained at the baseline, 5 week and 9 week visits. All study participants will be assigned a unique study ID number, and all blood samples, saliva samples, and laboratory paperwork will be identified with that number.

Blood collection will consist of a venous blood draw into of approximately 12 mL of blood (~2 tablespoons) into two EDTA (purple top) tubes and one finger stick collecting 5 drops of blood for a blood spot test.

These samples will be picked up by courier on the same day they are collected and transported to Doctor's Data, Inc for analysis.

Saliva sample collection will include approximately 2 mL collected from each participant. Participants will have abstained from food or beverages, except water, overnight prior to the collection. Participants will simply spit into a screw topped cryovial labeled with their study ID, date of collection, study time point, and approximate volume. If necessary, participants will be allowed up to 8 oz., of water in order to provide the sample, waiting at least 15 minutes between water intake and the sample collection. If necessary, cotton buccal cushions/swabs will be provided for participants to chew on to induce salivation.

E. HUMAN SUBJECTS RESEARCH

Protocol

Study Title: Methylation Diet and Lifestyle (MDL) Study

PI: [name], ND, MPH and [name], ND

IRB #: RB100217

Approval Date: 2.9.18

Ver. 1.1

E.1. Potential Risks

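### The 7pm eating cut-off in the intervention diet and the 10-12 hour pre-draw fast cannot both be kept for morning draws after 7am, so fasting length at weeks 5 and 9 can differ by arm

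*Protocol*

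**What the plan says.** - **Fast before blood draws, both arms.** The inclusion criteria in Protocol D.3.2 require willingness to "abstain from food or beverage intake for 10-12 hours before blood draws". This is the only fasting duration given in hours.
- **Eating window, intervention arm only.** The diet table in D.2.1 includes "Don't eat between 7pm and 7am, and at least 2 hours before bed". Below the table the protocol adds: "These recommendations serve as a guidance, while individual intake may vary based on preference".
- **Controls.** Under D.2, "The control group will undergo the same testing measures as the intervention group", but they "will not have access to the education information or be instructed to change diet or lifestyle factors". They have no evening cut-off.
- **When the diet starts.** D.5.9 places an introductory webinar before any of the changes begin. D.7.3 puts that webinar in the first study week and has men hold the supplements handed out at Visit 1 until after it. The cut-off therefore follows the baseline sample and is in force by weeks 5 and 9.
- **Sample collection.** D.8 states: "Fasting blood samples and saliva samples will be obtained at the baseline, 5 week and 9 week visits". In its saliva paragraph it adds: "Participants will have abstained from food or beverages, except water, overnight prior to the collection". Neither sentence gives a clock time for last intake or for the draw.
- **Use of the samples.** Table 4 schedules the Methylation Profile and the Folate Vitamer Panel at all three visits. They fall under D.4.4, headed "Exploratory Outcomes: Changes in biomarkers associated with methylation".

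**The concern.** The protocol requires a fast with a stated range, so it already treats time since last intake as something to hold steady at sampling. Its own diet instruction then works against this in one arm only, and only after baseline.

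A condition that is equal at Visit 1 and can differ by arm at Visits 2 and 3 enters directly into the between-arm comparison of change. If the intervention arm shows a shift in methionine-cycle intermediates or folate forms, part of it could reflect a longer fast on the morning of the draw and part the nine-week programme. Without recorded times the two could not be told apart. The possible gap also rises with adherence to the cut-off.

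There is a smaller inconsistency about water. D.3.2 bars all beverages before blood draws, while the saliva text in D.8 permits water, including up to 8 oz to help produce the sample. Blood and saliva are taken at the same visits, so a participant is not told clearly whether he may drink water.

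**Working it through.** The 10-12 hours is an instruction, not a derived figure, so there is nothing to reproduce. The check is clock arithmetic on the protocol's own rules.

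**Inputs**
- Last food at 7pm at the latest for a man who keeps the diet rule (D.2.1).
- Pre-draw fast of 10-12 hours (D.3.2).
- Draw time: not stated, so a range is shown.
- Control's last meal: not stated. The comparison is with a control who keeps the 10-12 hour rule.

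**Formula.** For a draw at morning hour t, the minimum time without food under the diet rule is (24 − 19) + t = 5 + t hours. The excess over a rule-keeping control runs from (5 + t) − 12 to (5 + t) − 10 hours.

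| Assumed draw | Minimum fast, 7pm cut-off kept | Within 10-12 h? | Excess over a control at 12 h to 10 h |
|---|---|---|---|
| 5am | 10 h | yes | −2 to 0 h |
| 6am | 11 h | yes | −1 to 1 h |
| 7am | 12 h | yes | 0 to 2 h |
| 8am | 13 h | no | 1 to 3 h |
| 9am | 14 h | no | 2 to 4 h |
| 10am | 15 h | no | 3 to 5 h |
| 11am | 16 h | no | 4 to 6 h |

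Both rules can be met on an overnight fast only for draws from 5am to 7am. For a 9am draw, the 10-12 hour rule puts last intake between 9pm and 11pm. A control is free to eat then; an intervention man is told not to.

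The excess is zero if the control also happens to stop at 7pm, although for a draw after 7am he too would then exceed 12 hours. At Visit 1 neither arm has the cut-off, so the rules create no expected gap.

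**What a gap could do to a test.** The protocol gives no figure for how these markers respond to extra fasting hours, so the shift b, in standard deviations, is purely assumed. With n men per arm, no programme effect, and a two-sided 5% test under the normal approximation:

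rejection rate = Φ(b/√(2/n) − 1.96) + Φ(−b/√(2/n) − 1.96)

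| Assumed b | n = 20 per arm (40 evaluated) | n = 24 per arm (48 randomised) |
|---|---|---|
| 0.1 SD | 6% | 6% |
| 0.2 SD | 10% | 11% |
| 0.3 SD | 16% | 18% |
| 0.5 SD | 35% | 41% |

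For example, with n = 20 and b = 0.2: √(2/20) = 0.316 and 0.2/0.316 = 0.632, so Φ(−1.328) + Φ(−2.592) ≈ 0.092 + 0.005 = 0.097. The table shows sensitivity only. It is not evidence that a shift of any of these sizes occurs.

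**The case against.** - **The gap is not shown to occur.** The protocol gives neither draw times nor the controls' eating times. This stands: the documents support saying that the fasts can differ, not that they do.
- **The diet is guidance.** D.2.1 says intake may vary, so the 7pm item is not a ban. This also stands, but adherence is actively sought. D.2.7.1 asks daily whether the man ate according to the programme, coaches check diet by telephone, and willingness to adhere is an inclusion criterion.
- **The night fast belongs to the assigned programme.** The randomised comparison estimates the effect of the whole package, including its eating window. This stands, so the comparison is not invalidated. What is lost is the ability to separate fasting on the sampling morning from the longer-term effect.
- **The 10-12 hours could be read as a minimum, and it appears only as a willingness item.** On that reading a 13-hour fast breaks no rule. The arms could still differ in length, because D.8 sets nothing tighter.
- **Visit instructions or the case report form may fix these times.** Possibly; they are not shown. But the conflicting instructions are in the protocol itself, so they need reconciling there.
- **The water conflict is slight.** The permission is in the saliva paragraph, whereas D.3.2 concerns blood. One clarifying sentence would settle it.

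A reader might go further and infer that the fasting biomarkers will differ by arm for this reason alone. The documents do not support that. The arms also differ in foods, exercise, stress practice and two supplements, and no figure links extra fasting hours to these markers.

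**Conclusion.** The point holds in a limited form. Read as a range, the 10-12 hour fast and the 7pm cut-off are incompatible for morning draws after 7am. The incompatibility falls on the intervention arm only and begins after baseline. Adherent intervention men can therefore be sampled at weeks 5 and 9 after a longer fast than controls: 1-3 hours longer at 8am and 2-4 hours longer at 9am, against a control within 10-12 hours. These sizes rest on assumed draw times and on adherence to both rules. The gap may be zero.

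The consequence is possible mixing of an acute fasting effect with the programme effect on the Methylation Profile and Folate Vitamer results. Its size on any marker is unknown. These outcomes are exploratory, and PROMIS-29 is unaffected. The point still merits a change because two stated rules collide in one arm and the protection is cheap.

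**What to change.** - Reconcile D.2.1, D.3.2 and D.8 by stating one pre-draw fasting condition that applies identically to both arms at all three visits, and say that it governs the evening before a draw. The length and clock times are for the investigators to choose.
- State once whether water is allowed before the combined blood and saliva collection.
- Record time of last intake and time of draw on the case report form, if it does not already do so.
- Use hours fasted in a sensitivity analysis of the Methylation Profile and Folate Vitamer results. Because hours fasted may itself follow from the assigned diet, keep this as a supporting analysis and not a replacement for the comparison by randomised arm.

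The cost is wording changes, two time fields, slightly tighter visit scheduling, and evening instructions for controls before each draw.

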- Able to speak, read and understand English

Exclusion criteria:

- Currently taking any of the following prescription medications
 - Proton pump inhibitors: omeprazole (Prilosec, Prilosec OTC); aspirin and omeprazole (Yosprala); lansoprazole (Prevacid, Prevacid IV, Prevacid 24-Hour); dexlansoprazole (Dexilent, Dexilent Solutab); rabeprazole (Aciphex, Aciphex Sprinkle); pantoprazole (Protonix)

Protocol

Study Title: Methylation Diet and Lifestyle (MDL) Study

PI: [name], ND, MPH and [name], ND

IRB #: RB100217

Approval Date: 2.9.18

Ver. 1.1

- H2-blockers: nizatidine (Axid, Axid AR, Axid Pulvules); famotidine (Pepcid, Pepcid AC); cimetidine (Tagamet, Tagamet HB); ranitidine (Zantac)
- These classes of medications are excluded due to direct (due to nutrient requirements for metabolism) and indirect (through impaired digestion and assimilation of nutrients).
- Use of nutrition supplements or herbal products not prescribed by a licensed healthcare provider for a medical condition
- Currently following a prescribed dietary/lifestyle program or initiate within the 30 days prior to baseline
- Initiation of or changes to an exercise regimen within 30 days prior to baseline
- Use of nicotine, marijuana or cannabinoids (including CBD products) or recreational drugs/substances (such as but not limited to cocaine, phencyclidine [PCP], and methamphetamine) current/within the last 30 days or use during the study
- Have a diagnosis of cardiovascular disease, kidney disease, liver disease, diabetes, autoimmune disease, high blood pressure, or cancer (does not include *basal cell carcinoma, squamous cell carcinoma, and/or carcinoma in situ of the cervix*).
- Have a diagnosis of an immunodeficiency condition, such as Human Immunodeficiency Virus (HIV) infection or Acquired Immune Deficiency Syndrome (AIDS)
- Have a diagnosis of neurodegenerative conditions such as, amyotrophic lateral sclerosis (ALS), Parkinson’s disease, Multiple Sclerosis, or Alzheimer’s disease.
- Excessive alcohol consumption (more than 4 drinks per day or 14 per week on average)
- Known sensitivity, intolerance or allergy to ingredients in the study supplements or in the recommended dietary therapy
- Currently receiving intravenous nutrient therapy
- Currently participating in another interventional research study or participated in another interventional study within the last 3 weeks prior to baseline

D.4 Outcome Measures

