Once a participant is deemed eligible and provided signed consent, the study staff will determine randomization order using a random number generator (randomization.com). After enrollment, the study coordinator will select the next sequential envelope from the locked filing cabinet within the study site office. The study staff will write the current date and participant initials on the bottom right corner of the envelope and open the envelope and retrieve its contents. The envelope contents will show which cohort the participant is assigned to, with intervention or control. This will be assigned to the participant ID number and entered into REDCap.

D.5.7. Washout Period

Study participants assigned to the intervention group will be asked to refrain from taking any over-the-counter supplements, medications or herbal products, except short-term use (<1 week) and at least 1 week before scheduled study visits, alcohol, nicotine, marijuana or cannabinoids (including CBD products) or recreational drugs/substances for 3 weeks before the baseline visit. Written instructions will be provided.

D.5.8. Study Visits

There will be 3 in-person study visits for all participants during the 9-week study.

Baseline/Study Visit 1 (Week 1)

The following procedures, evaluation and/or assessments will be obtained at Study Visit 1:

- Height and weight
- Vital signs including heart rate, blood pressure, respiration rate and temperature

Protocol

Study Title: Methylation Diet and Lifestyle (MDL) Study

PI: [name], ND, MPH and [name], ND

IRB #: RB100217

Approval Date: 2.9.18

Ver. 1.1

- Questionnaires including Lifestyle Habits, PROMIS-29, MYMOP, MSQ, and NUNM Adverse Events, VioScreen
- Blood draw to collect 2 tubes of blood
- Finger stick to collect 5 drops of blood
- Saliva sample
- If in intervention group, will receive study supplements for first 4 weeks and instructions on how and when to take
- Case report form completed by study staff
- Waist-to-hip ratio will be calculated using the following methods:
 - Participant with stand up straight and breathe out. Use a tape measure to check the distance around the smallest part of the waist, just above the umbilicus. This is the waist circumference.
 - Measure the distance around the largest part of the hips — the widest part of the buttocks. This is the hip circumference.
 - Calculate the waist-to-hip ratio by dividing the waist circumference by the hip circumference.

Study Visit 2 (Week 5)

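### The protocol excludes users of non-prescribed supplements but also washes them out after randomisation, in one arm only, and its 3-week washout guarantees only 7 clean days

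*Protocol*

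**What the plan says.** **Entry.** The exclusion list in Protocol D.3.2 contains "Use of nutrition supplements or herbal products not prescribed by a licensed healthcare provider for a medical condition". It gives no look-back period and makes no provision for men who stop. The inclusion list asks that men be "Willing to avoid any over-the-counter medications, supplements or herbal products for the length of the study", with an exception for brief use away from visits.

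**Order of events.** Eligibility is verified at the screening visit (D.5.4). Randomisation by envelope follows for men found eligible (D.5.1, D.5.6). Visit 1, the baseline, comes after that.

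**Washout.** D.2 states: "The intervention group will undergo a 3-week washout period following the discontinuation of any non-medically required nutrition or herbal supplements". D.5.7 applies to men assigned to the intervention. It asks them to refrain from over-the-counter supplements, medicines and herbal products, "except short-term use (<1 week) and at least 1 week before scheduled study visits", and from alcohol, nicotine, cannabis and "recreational drugs/substances for 3 weeks before the baseline visit". Neither section states a washout for controls, and D.2 says controls are not told to change diet or lifestyle.

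**Measurements.** The Methylation Profile (including SAM/SAH) and the Folate Vitamer Panel are taken at Visits 1, 2 and 3 (Table 4). Both are exploratory outcomes. The primary outcome is PROMIS-29.

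**The concern.** D.2 gives randomised men time to clear products whose users D.3.2 has already turned away. A screener following D.3.2 rejects a man who takes a multivitamin on his own initiative. A screener following D.2 enrols him, randomises him and has him stop. Both could defend the decision from the text, and they would produce different samples and different baselines.

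The second reading raises a question of comparability. Supplements that contain folate or other methyl donors act on the pathway being measured: section C.1 itself calls 5-MTHF a key substrate. Stopping them may move the folate vitamers and SAM/SAH. If stopping were equal in both arms, randomisation would take care of it. Here it is prescribed before baseline, after allocation, and for one arm only.

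The length of the washout is also stated in two ways that do not agree.

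**Working it through.** **1. Can a user of non-prescribed supplements enter?**

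| Section | Applies to | What follows for a current user |
|---|---|---|
| D.3.2, exclusion | everyone, before randomisation | not eligible, whenever the use occurred |
| D.2 | intervention arm, after randomisation | enrolled, stops, 3-week washout |
| D.5.7 | intervention arm, after randomisation | asked to refrain for 3 weeks before Visit 1 |

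If D.3.2 governs, practically nobody has anything to discontinue under D.2. If D.2 governs, the D.3.2 exclusion is not being applied. The protocol does not say which prevails.

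**2. How long is the guaranteed clean period?**

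Inputs: a 3-week washout (D.2, D.5.7); permitted use of under 1 week that stops at least 1 week before a visit (D.5.7). I number days backwards from Visit 1 and count the protected week as seven whole days.

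- Stated washout: 3 × 7 = 21 days, from day −21 to day −1. This is D.2's figure, and it holds if there is no exception.
- Last day on which use is permitted: day −8.
- Days of the washout on which use may fall: day −21 to day −8, that is 14 of 21.
- Latest single permitted episode, 6 whole days: days −13 to −8.
- Clean days left before Visit 1: 7, and 7/21 = 33% of the stated length.

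One permitted episode is enough to give this result. It does not depend on how many episodes the exception allows.

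**3. What does a one-arm washout do to change from baseline?**

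Let p be the proportion of users at screening, equal in both arms by randomisation. Let δ be the mean shift in a marker once a user's stopping has taken full effect, w the fraction of that shift reached by Visit 1 in the washed-out arm, and τ the true intervention effect. Assume that effects add, that stopping has taken full effect by Week 9, and that no supplements are used between visits.

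Mean change in the intervention arm, Visit 1 to Week 9: τ + (1 − w)pδ.

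| What controls do | Control change | Difference in change | Baseline difference between arms |
|---|---|---|---|
| Stop before Visit 1, same schedule | (1 − w)pδ | τ | 0 |
| Stop at Visit 1 | pδ | τ − wpδ | wpδ |
| Do not stop | 0 | τ + (1 − w)pδ | wpδ |

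Only the first row gives τ in general, and it is the row for which the protocol gives controls no instruction. The second follows if the inclusion criterion's commitment begins with the 9-week study. The third follows if controls simply carry on. The error can take either sign. In the third row it vanishes only when washout is complete by Visit 1 (w = 1), and a shorter guaranteed clean period makes that less certain.

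The documents give no value for p, δ or w, so the size cannot be computed. If D.3.2 is enforced literally, p is close to 0 and so is the bias.

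**The case against.** **The sections can be partly harmonised.** D.5.7 asks men to refrain, which a man who never used supplements can also do, so as an instruction to stay abstinent it is compatible with D.3.2. That is fair for D.5.7. It does not rescue D.2, which places the washout after the products are discontinued and so assumes that there was use to stop.

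**The exception is disclosed.** It stands in D.5.7 and in the inclusion criterion, and D.2 may simply be a shorter summary. That stands: nothing is concealed, and the mismatch is between D.2 and D.5.7. The 7 days are a worst case under permitted use, not a prediction. D.6 also makes starting an excluded supplement a withdrawal category, so repeated use should not be assumed to be unlimited.

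**The inclusion criterion binds both arms.** Controls too must be willing to avoid these products. But it runs for the length of the study, which D.5.8 describes as 9 weeks with Visit 1 at its start. It does not clearly require controls to stop before baseline.

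**The stakes are limited.** The markers most exposed are exploratory, and the share of men affected is unknown. Both points stand.

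Three stronger readings are tempting, and the documents do not support them:

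- *Nicotine, cannabis and recreational drugs.* A reader might infer the same contradiction, because D.3.2 excludes "Use of nicotine, marijuana or cannabinoids (including CBD products) or recreational drugs/substances" with the window "current/within the last 30 days or use during the study" and D.5.7 asks for 3 weeks' abstention. Excluding users and asking entrants to stay abstinent are compatible. The windows differ (30 − 21 = 9 days), but one is an entry look-back and the other a pre-baseline instruction. D.2 does not mention these substances.
- *Prescribed folate products.* A reader might infer that such a man fails the inclusion criterion and passes the exclusion. If over-the-counter qualifies the whole list in the inclusion criterion, as it qualifies supplements in D.5.7, there is no conflict.
- *The enrolled population.* A reader might infer that it differs from the one stated. The text leaves it undetermined and shows no more than that.

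**Conclusion.** The point holds for non-prescribed supplements and herbal products. D.3.2 excludes their users without a time window, while D.2 and D.5.7 provide for washing them out after randomisation, so the entry rule is undetermined. If users enter, Visit 1 is measured under different conditions by arm, and change from baseline in the folate vitamers and SAM/SAH can be biased in either direction. This rests on the washout applying to the intervention arm only, as both sections say, and on controls not stopping on the same schedule before Visit 1. The amount of bias cannot be stated from the documents, and it is negligible if D.3.2 is enforced as written.

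Separately, the 21-day washout in D.2 becomes 7 guaranteed days under D.5.7. This assumes that the exception covers supplements and herbals, as its place in the sentence indicates.

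PROMIS-29 is also first measured after this washout, but no effect on it is shown. The correction is worth making before enrolment because screening staff must apply these sections directly. It is not a fatal flaw.

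**What to change.** - Reconcile D.2, D.3.2 and D.5.7 to a single entry rule for non-prescribed supplements and herbal products, stating whether a user may enter after stopping. Which rule is for the sponsor and investigators to decide.
- If users may enter, have any supplement-free period apply equally to both arms and be completed before the randomisation envelope is opened. Visit 1 is then comparable by design. If they may not, remove the reference to discontinuation from D.2.
- Make D.2 and D.5.7 agree on whether the short-use exception covers supplements and herbals within the washout, and align the inclusion criterion with the answer.

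The cost is a wording amendment and a revised screening script. The one practical downside is that a supplement user who may enter waits out the period before he is randomised.
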